6.16. Protocol Deviations 73

6.17. Interim Analyses and Data Monitoring 74

 6.17.1. Interim Analysis Plan 74

6.18. Planned Exploratory Analyses 75

6.19. Annual Report Analyses 75

6.20. Clinical Trial Registry Analyses 75

7. Unblinding Plan 77

8. References 78

Table of Contents

Table	Page
Table JAHM.5.1. Geographic Regions for Stratification	13
Table JAHM.6.1. Imputation Techniques for Various Variables	21
Table JAHM.6.2. Seed Values for Multiple Imputation	24
Table JAHM.6.3. Seed Values for Imputation.....	26
Table JAHM.6.4. Description and Derivation of Primary, Secondary and Exploratory Efficacy Outcomes	37
Table JAHM.6.5. Description of Primary, Secondary and Exploratory Efficacy Analyses	41
Table JAHM.6.6. Description and Derivation of Health Outcomes and Quality-of-Life Measures	45
Table JAHM.6.7. Description of Health Outcomes and Quality-of-Life Measures Analyses	52
Table JAHM.6.8. Categorical Criteria for Abnormal Treatment-Emergent Blood Pressure and Pulse Measurement, and Categorical Criteria for Weight Changes for Adults	61

Table of Contents

Figure	Page
Figure JAHM.5.1. Illustration of study design for Clinical Protocol I4V-MC-JAHM.	12
Figure JAHM.6.1. Illustration of graphical multiple testing procedure with initial α allocation and weights.	30

3. Revision History

Statistical Analysis Plan (SAP) Version 1 is based on Protocol I4V-MC-JAHM(a) and was approved prior to the production transfer for the first DMC meeting. SAP Version 2 was approved prior to the final database lock and includes the following changes:

- added additional exploratory objective for TCS use
- added follow-up population definition
- removed details included in the standards
- updated daily diaries to use an interval mean weekly score
- updated baseline and post-baseline algorithm for actigraphy to use time
- updated frequency of itch and skin pain to use 28-day visit intervals
- added estimand language
- added additional details for MMRM and ANCOVA
- added time to event analysis
- added baseline value to logistic regression model
- added seed values for tipping point
- updated diagnosis age group categories
- updated definition for deriving age and diagnosis age
- added BMI category, weight category and PGI-S-AD to baseline summaries
- added 2 cyclosporine subset definitions and revised existing subset definition; added to baseline summaries
- updated seed values for pMI
- added overall summary of rescue therapies
- clarified sensitivity analyses for PPS, pMI and tipping point in Tables JAHM.6.4 and JAHM.6.6
- removed comparisons in Table JAHM.6.6 when not needed
- updated mapping of ET visits to closest, not next visit
- added definition for safety baseline for clarity
- added sensitivity analysis for safety to censor on last dose of study drug for rescue to systemics
- update exposure ranges from weeks to days
- removed temporary interruption of study drug to AE or lab from overview of AE table
- removed mention of incidence-rates, including exposure adjusted incidence rates
- updated to refer to compound level safety standards instead of PSAP
- added PT for malignancy
- provided clarity that CSSRS summary will be created when positive responses happen during treatment
- updated subgroup analyses
- added a Cox proportional hazard (CPH) model of minimum time (in days) to 4-point itch reduction with effects for treatment, region (where applicable), baseline mean itch, and disease severity to section 6.2.3
- updated the graphical approach

4. Study Objectives

4.1. Primary Objective

The primary objective of this study is to test the hypothesis that baricitinib 4-mg once daily (QD) or baricitinib 2-mg QD is superior to placebo in the treatment of patients with moderate to severe atopic dermatitis (AD), as assessed by the proportion of patients achieving the validated Investigator's Global Assessment for AD (vIGA-AD, referred to throughout the SAP as IGA) of 0 or 1 with a ≥ 2 -point improvement at Week 16.

In particular, the associated estimand for this objective is to measure the effect of therapy with baricitinib as assessed by the proportion of patients with a response of IGA 0 or 1 at Week 16 assuming treatment response disappears after patients are rescued or discontinued from the study or treatment. See Sections 6.4.1 and 6.11.1 on how this estimand handles outcomes after the occurrence of any intercurrent event through nonresponder imputation (NRI).

4.2. Secondary Objectives

4.2.1. Key Secondary Objectives

These are prespecified objectives that will be adjusted for multiplicity.

Objectives	Endpoints
To test the hypothesis that baricitinib 1-mg QD is superior to placebo in the treatment of patients with moderate to severe AD.	
 Proportion of patients achieving IGA of 0 or 1 with a ≥ 2-point improvement at Week 16
To compare the efficacy of baricitinib 1-mg QD, 2-mg QD, or 4-mg QD to placebo in AD during the 16-week double-blind placebo-controlled treatment period as measured by improvement in signs and symptoms of AD.	
 Proportion of patients achieving EASI75 at 16 weeks Proportion of patients achieving EASI90 at 16 weeks Percent change from baseline in EASI score at 16 weeks Proportion of patients achieving SCORAD75 at 16 weeks
To compare the efficacy of baricitinib 1-mg QD, 2-mg QD, or 4-mg QD to placebo in AD during the 16-week double-blind placebo-controlled treatment period as assessed by patient-reported outcome measures.	
 Proportions of patients achieving a 4-point improvement from baseline in Itch NRS at 1 week, 2 weeks, 4 weeks, and 16 weeks Mean change from baseline in the score of Item 2 of the ADSS at 1 week and 16 weeks Mean change from baseline in Skin Pain NRS at 16 weeks

4.2.2. Other Secondary Objectives

These are prespecified objectives that will not be adjusted for multiplicity.

Objectives	Endpoints
To test the hypothesis that baricitinib 1-mg QD, 2-mg QD, or 4-mg QD is superior to placebo in the treatment of patients with moderate to severe AD.	
 • Proportion of patients achieving IGA of 0 or 1 with a ≥ 2-point improvement at Week 4
To compare the efficacy of baricitinib 1-mg QD, 2-mg QD, or 4-mg QD to placebo in AD during the 16-week double-blind placebo-controlled period as measured by physician-assessed signs and symptoms of AD.	
 • Proportion of patients achieving EASI50 at 16 weeks • Proportion of patients achieving IGA of 0 at 16 weeks • Mean change from baseline in SCORAD at 16 weeks • Proportion of patients achieving SCORAD90 at 16 weeks • Mean change from baseline in BSA affected at 16 weeks • Proportion of patients developing skin infections requiring antibiotic treatment by Week 16
To compare the efficacy of baricitinib 1-mg QD, 2-mg QD, or 4-mg QD to placebo in AD during the 16-week, double-blind, placebo-controlled treatment period as assessed by patient-reported outcome/QoL measures.	
 • Percent change from baseline in Itch NRS at 1 week and 16 weeks • Mean change from baseline in Itch NRS at 4 weeks and 16 weeks • Mean change from baseline in the total score of the POEM at 16 weeks • Mean change in the PGI-S-AD scores at 16 weeks • Mean change from baseline in HADS at 16 weeks • Mean change in the DLQI scores at 16 weeks • Mean change in the WPAI scores at 16 weeks • Mean change in the EQ-5D-5L scores at 16 weeks

4.3. Exploratory Objectives

The exploratory objectives of this study are the following:

Objectives/Endpoints

• Mean change from baseline in nocturnal itch assessed by actigraphy device at 1 week and 4 weeks• Frequency of patient-reported “no itch” (Itch NRS score = 0) days from daily diaries from Week 12 to Week 16• Frequency of patient-reported “no pain” (Skin Pain NRS score = 0) days from daily diaries from Week 12 to Week 16• Mean change from baseline in the score of Item 1 of the ADSS at 1 week and 16 weeks• Mean change from baseline in the score of Item 3 of the ADSS at 1 week and 16 weeks• To evaluate changes from baseline in immunoglobulin E levels during the study• To evaluate changes from baseline in eosinophil levels during the study• To characterize baricitinib pharmacokinetics in the AD population and explore relationships between baricitinib exposure and study endpoints• To assess time to 4-pt itch reduction during the first 14 days after initiation of treatment• To assess time to improvement in Skin Pain during the first 14 days after the initiation of treatment• To assess the use of rescue therapy through the weight of sponsor provided topical corticosteroid and number of days not using rescue therapy

5. Study Design

5.1. Summary of Study Design

Study I4V-MC-JAHM (JAHM) is a Phase 3, multicenter, randomized, double-blind, placebo-controlled, parallel-group, outpatient study evaluating the efficacy and safety of baricitinib 1-mg once daily (QD), 2-mg QD, and 4-mg QD as compared to placebo in adult patients with moderate to severe AD. The study is divided into 3 periods, a 5-week Screening period, a 16-week Double-Blinded Treatment period, and a 4-week Post-Treatment Follow-Up period. For those patients who complete the 16-week treatment period, there is an option to participate in the long-term extension study I4V-MC-JAHN (JAHN).

Approximately 600 patients ≥ 18 years of age who have responded inadequately to or who are intolerant to topical therapy will be randomized at a 2:1:1:1 ratio to receive placebo QD, baricitinib 1-mg QD, baricitinib 2-mg QD, or baricitinib 4-mg QD (240 patients in the placebo group; 120 patients in each baricitinib treatment group). Patients will be stratified at randomization according to disease severity (IGA 3 vs. 4) and geographic region.

Study JAHM will consist of 3 periods:

- Period 1: Screening period is between 8 and 35 days prior to Week 0 (Visit 2)
- Period 2: Double-Blind, Placebo-Controlled Treatment period from Week 0 (Visit 2) through Week 16 (Visit 8)
- Period 3: Post-Treatment Follow-Up period from last treatment visit at Week 16 (Visit 8) or Early Termination Visit (ETV) to approximately 28 days after the last dose of investigational product

[Figure JAHM.5.1](#) illustrates the study design. The blinding procedure is described in the Protocol.

[figure not shown]

Figure JAHM.5.1. Illustration of study design for Clinical Protocol I4V-MC-JAHM.

Abbreviations: AD = atopic dermatitis; eGFR = estimated glomerular filtration rate; PPD = purified protein derivative; QD = once daily; V = visit; W = week.

- Applicable to patients taking topical treatments (excluding emollients) or systemic treatments for AD at the time of screening.
- For patients randomized to the 4-mg once daily dose who have renal impairment (defined as eGFR <60 mL/min/1.73 m²), the baricitinib dose will be 2-mg once daily.
- Patients for whom PPD skin test for the evaluation of tuberculosis infection was performed at V1 must return and PPD test must be read 48 to 72 hours after Visit 1 (post-PPD).
- Occurs approximately 28 days after the last dose of investigational product. Not required for those patients entering the long-term extension study JAHN.

5.2. Method of Assignment to Treatment

Patients who meet all criteria for enrollment will be randomized in a 2:1:1:1 ratio (placebo, baricitinib 1-mg; baricitinib 2-mg; baricitinib 4-mg) to double-blind treatment at Visit 2 (Week 0). Randomization will be stratified by geographic region (Europe [EU], Japan [JPN], rest-of-world [ROW]) and disease severity at baseline (IGA 3 vs. 4). Assignment to treatment groups will be determined by a computer-generated random sequence using an interactive web-response system (IWRS). The IWRS will be used to assign blister packs, each containing double-blind investigational product tablets to each patient, starting at Visit 2 (Week 0), and at each visit up to and including Visit 7 (Week 12). Site personnel will confirm that they have located the correct blister packs by entering a confirmation number found on the blister packs into the IWRS.

This study will be conducted internationally in multiple sites. [Table JAHM.5.1](#) describes how regions will be defined for stratification. Regions may be combined for statistical analyses in the case when one of the region strata fails to meet the required minimum number of 30 patients. The 2 region strata with the least number of patients will then be pooled.

Table JAHM.5.1. Geographic Regions for Stratification

Region	Countries
Europe	Austria, Hungary, Poland, Spain, Switzerland
Japan	Japan
Rest of World	Argentina, Australia, Israel, Korea

6. A Priori Statistical Methods

6.1. Determination of Sample Size

Study JAHM will aim to enroll approximately 600 patients ≥ 18 years of age. The proposed sample size will ensure a $>90\%$ power to detect any difference between the baricitinib 4-mg and placebo treatment groups and the baricitinib 2-mg and placebo treatment groups, each using a 2-sided alpha of 0.05, assuming 10% placebo, 25% baricitinib 2-mg, and 30% baricitinib 4-mg response rates for the primary endpoint. The assumptions are based on what was observed in the Phase 2 Study (I4V-MC-JAHG). The proposed end point of IGA 0 or 1 represents patients whose AD is clear or almost clear from a baseline of moderate or severe disease. The anticipated effect size represents 3 times more patients achieving this benefit compared to placebo, which in discussion with therapeutic experts, is of a magnitude that is considered clinically relevant.

Sample size and power estimates were obtained from nQuery® Advisor 7.0.

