6.6. Multiple Comparisons/Multiplicity

The primary and key secondary endpoints will be adjusted for multiplicity in order to control the overall family-wise Type I error rate at a 2-sided alpha level of 0.05.

The following is a list of primary and key secondary endpoints to be tested. The subscript for **H** denotes dose (4-mg, 2-mg, 1-mg), the numerical identifier of the endpoint within the dose, and the type of hypothesis (0 for null, 1 for alternative), respectively.

Primary Null Hypotheses:

- **H_{4,1,0}**: Proportion of baricitinib 4-mg patients achieving IGA of 0 or 1 with a ≥ 2 -point improvement from baseline at Week 16 is less than or equal to the proportion of placebo patients achieving IGA of 0 or 1 with a ≥ 2 -point improvement from baseline at Week 16
- **H_{2,1,0}**: Proportion of baricitinib 2-mg patients achieving IGA of 0 or 1 with a ≥ 2 -point improvement from baseline at Week 16 is less than or equal to the proportion of placebo patients achieving IGA of 0 or 1 with a ≥ 2 -point improvement from baseline at Week 16

Key Secondary Null Hypotheses:

- **H_{4,2,0}**: Proportion of baricitinib 4-mg patients achieving EASI75 is less than or equal to the proportion of placebo patients achieving EASI75 at Week 16 [EASI75]
- **H_{4,3,0}**: Proportion of baricitinib 4-mg patients achieving a 4-point improvement in Itch NRS is less than or equal to the proportion of placebo patients achieving a 4-point improvement in Itch NRS at Week 16 [ITCH W16]
- **H_{4,4,0}**: Percent change from baseline in EASI score for baricitinib 4-mg patients is greater than or equal to the percent change from baseline in EASI score for placebo patients at Week 16 [EASI PCFB]
- **H_{4,5,0}**: Proportion of baricitinib 4-mg patients achieving a 4-point improvement in Itch NRS is less than or equal to the proportion of placebo patients achieving a 4-point improvement in Itch NRS at Week 4 [ITCH W4]
- **H_{4,6,0}**: Proportion of baricitinib 4-mg patients achieving SCORAD75 is less than or equal to the proportion of placebo patients achieving SCORAD75 at Week 16 [SCORAD75]
- **H_{4,7,0}**: Proportion of baricitinib 4-mg patients achieving EASI90 is less than or equal to the proportion of placebo patients achieving EASI90 at Week 16 [EASI 90]
- **H_{4,8,0}**: Mean change from baseline in Skin Pain NRS for baricitinib 4-mg patients is greater than or equal to the mean change from baseline in Skin Pain NRS for placebo patients at Week 16 [PAIN W16]

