- **H_{1,8,0}**: Mean change from baseline in Skin Pain NRS for baricitinib 1-mg patients is greater than or equal to the mean change from baseline in Skin Pain NRS for placebo patients at Week 16 [PAIN W16]
- **H_{1,9,0}**: Mean change from baseline in the score of Item 2 of the ADSS for baricitinib 1-mg patients is greater than or equal to the mean change from baseline in the score of Item 2 of the ADSS for placebo patients at Week 16 [ADSS2 W16]
- **H_{1,10,0}**: Proportion of baricitinib 1-mg patients achieving a 4-point improvement in Itch NRS is less than or equal to the proportion of placebo patients achieving a 4-point improvement in Itch NRS at Week 2 [ITCH W2]
- **H_{1,11,0}**: Mean change from baseline in the score of Item 2 of the ADSS for baricitinib 1-mg patients is greater than or equal to the mean change from baseline in the score of Item 2 of the ADSS for placebo patients at Week 1 [ADSS2 W1]
- **H_{1,12,0}**: Proportion of baricitinib 1-mg patients achieving a 4-point improvement in Itch NRS is less than or equal to the proportion of placebo patients achieving a 4-point improvement in Itch NRS at Week 1 [ITCH W1]

The multiple testing procedure is specified by [Figure JAHM.6.1](#).

[figure not shown]

Figure JAHM.6.1. Illustration of graphical multiple testing procedure with initial α allocation and weights.

The primary null hypotheses includes testing whether each of the baricitinib 4-mg and the baricitinib 2-mg dose is less than or equal to placebo at the primary endpoint defined as the proportion of placebo patients achieving IGA of 0 or 1 and ≥ 2 point improvement from baseline at Week 16. The initial alpha allocation is split so that $H_{4,1,0}$ has 0.04 and $H_{2,1,0}$ and 0.01. Together with these primary hypotheses, multiplicity adjusted analyses will be performed on key secondary null hypotheses to control the overall family wise Type I error rate at a 2-sided alpha level of 0.05. The graphical multiple testing procedure described in Bretz et al. (2011), which is a closed testing procedure will be used; hence it strongly controls the family-wise error rate across all endpoints (Alosh et al. 2014).

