If $H_{4,1,0}$ and $H_{2,1,0}$ are not rejected, no further testing is conducted as the α for that test is considered “spent” and cannot be passed to other endpoints. If $H_{4,1,0}$ or $H_{2,1,0}$ is rejected, the testing process continues in either branches (starting with $H_{4,1,0}$ and $H_{2,2,0}$ respectively), with α propagated according to the weights on the corresponding edges displayed in [Figure JAHM.6.1](#), as long as each hypothesis in the sequence can be rejected at its allocated α level. Each time a hypothesis is rejected, the graph is updated to reflect the reallocation of α , which is considered “recycled” by Alosch et al. (2014). This iterative process of updating the graph and reallocating α is repeated until all hypotheses have been tested or when no remaining hypotheses can be rejected at their corresponding α levels.

For Japan, the same testing strategy described in the [Figure JAHM.6.1](#) will be used, however, the proportion of patients achieving EASI75 and IGA of 0 or 1 at Week 16 are considered co-primary. Both endpoints have to meet statistical significance compared with placebo with a specific α level based on the graphical multiple testing procedure in order to demonstrate a superiority of a given baricitinib dose (baricitinib 4-mg and/or baricitinib 2-mg) compared with placebo. That is, $H_{4,1,0}$ and $H_{4,2,0}$ have to be rejected in order to demonstrate the superiority of baricitinib 4-mg compared with placebo and $H_{2,1,0}$ and $H_{2,2,0}$ have to be rejected in order to demonstrate the superiority of baricitinib 2-mg compared with placebo.

There will be no adjustment for multiple comparisons for any other analyses.

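### The >90% power claimed for baricitinib 2-mg is calculated at alpha 0.05, but that primary hypothesis starts at 0.01, where power is about 86%

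*SAP*

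**What the plan says.** SAP Section 6.1 makes one power claim covering two comparisons, 4-mg and 2-mg each against placebo: "The proposed sample size will ensure a $>90\%$ power to detect any difference". It gives the inputs as "each using a 2-sided alpha of 0.05, assuming 10% placebo, 25% baricitinib 2-mg, and 30% baricitinib 4-mg response rates". It mentions neither a division of alpha between the doses nor any later reallocation.

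Section 5.1 gives the arm sizes: "240 patients in the placebo group; 120 patients in each baricitinib treatment group".

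Section 6.6 sets a different level for these two tests. The primary and key secondary hypotheses are adjusted together to "control the overall family-wise Type I error rate at a 2-sided alpha level of 0.05". Within that total, "The initial alpha allocation is split so that $H_{4,1,0}$ has 0.04 and $H_{2,1,0}$ and 0.01" (the second "and" evidently means "has"). After a rejection, alpha is "propagated according to the weights on the corresponding edges displayed in" Figure JAHM.6.1. The figure is not reproduced in the text at hand, so its weights are unknown here.

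Section 6.2 makes 0.05 the default significance level and names the Section 6.6 graph as an exception. Which alpha governs the tests is therefore clear; the power statement does not use it.

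**The concern.** Two hypotheses that share a family-wise 0.05 cannot both start at 0.05. The 2-mg hypothesis starts at one fifth of the level used to justify its power.

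The 2-mg comparison is one of only two primary hypotheses, so its power is a design property that readers will rely on. Section 6.1 implies a chance below 10% of missing the assumed 15-point difference. At the alpha actually assigned at the start, that chance is about 14%. For Japan, Section 6.6 requires both the IGA and the EASI75 hypotheses to be rejected before a dose is called superior. Power for that conclusion cannot exceed power for the IGA hypothesis alone, so an overstated IGA figure carries over.

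**Working it through.** **Inputs.** Placebo n0 = 240 and 2-mg or 4-mg n1 = 120 (Section 5.1). Response rates are 10%, 25% and 30% (Section 6.1). Initial two-sided alphas are 0.04 for 4-mg and 0.01 for 2-mg (Section 6.6). There is no dropout adjustment: missing outcomes count as nonresponse, so all randomized patients stay in the denominator.

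**Formula** (two proportions, variance pooled under the null):

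- p̄ = (n0·p0 + n1·p1)/(n0 + n1)
- SE0 = √[p̄(1 − p̄)(1/n0 + 1/n1)]
- SE1 = √[p0(1 − p0)/n0 + p1(1 − p1)/n1]
- power = Φ[(p1 − p0 − z·SE0)/SE1], with z = z(1 − α/2)

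**Step 1: reproduce the SAP's figure (2-mg, alpha 0.05).** p̄ = (24 + 30)/360 = 0.15. SE0 = √(0.1275 × 0.0125) = 0.03992. SE1 = √(0.09/240 + 0.1875/120) = 0.04402. Power = Φ[(0.15 − 1.960 × 0.03992)/0.04402] = Φ(1.630) = 94.8%. The claim of more than 90% is correct on its own inputs.

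**Step 2: 2-mg at its initial alpha of 0.01.** Power = Φ[(0.15 − 2.576 × 0.03992)/0.04402] = Φ(1.072) = 85.8%.

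**Step 3: 4-mg at its initial alpha of 0.04.** p̄ = 60/360 = 0.1667, SE0 = 0.04167, SE1 = 0.04610. Power = Φ[(0.20 − 2.054 × 0.04167)/0.04610] = Φ(2.482) = 99.3%. Fisher's exact test gives 99.4%. The 4-mg claim survives the split.

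**Step 4: does the choice of test matter?** 2-mg power by method:

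| Method | alpha 0.05 | alpha 0.01 |
|---|---|---|
| Pooled normal | 94.8% | 85.8% |
| Pearson chi-square, exact enumeration | 95.4% | 86.5% |
| Wald log odds ratio, 0.5 added to each cell | 95.4% | 86.3% |
| Fisher's exact | 94.4% | 84.3% |
| Continuity-corrected normal | 93.2% | 82.4% |
| Unpooled normal | 92.6% | 79.7% |

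Every method is above 90% at 0.05 and below 90% at 0.01. The pooled formula reaches 90% at an alpha of about 0.019, nearly twice the initial allocation.

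**Step 5: how much recycling would be needed?** The weights are unknown, so this step assumes that a share r of the 0.04 passes directly to the 2-mg primary hypothesis when 4-mg is rejected at 0.04. The 2-mg hypothesis is then tested at 0.01 + 0.04r. The shared placebo arm is taken into account.

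| Share r | 2-mg alpha after 4-mg rejection | Power, Pearson | Power, Fisher |
|---|---|---|---|
| 0% | 0.010 | 86.5% | 84.3% |
| 15% | 0.016 | 89.8% | 88.1% |
| 20% | 0.018 | 90.8% | 88.7% |
| 30% | 0.022 | 91.7% | 90.0% |
| 50% | 0.030 | 93.3% | 91.8% |
| 100% | 0.050 | 95.3% | 94.3% |

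Power reaches 90% at a share of about 17–18% by Pearson and about 30% by Fisher. If alpha returns only after further rejections in the 4-mg branch, the gain is smaller than shown.

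**Step 6: the overall objective.** With the initial split and no recycling, the Pearson test rejects at least one primary hypothesis with probability about 99.8% and both with probability about 86%.

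**The case against.** The best defence is that 86% is a floor. Under the SAP's assumptions 4-mg is rejected more than 99% of the time. If the graph then sends even a moderate share of its alpha to the 2-mg primary hypothesis, power passes 90%, and full return gives about 94–95%. Without the figure, nobody can show that the >90% claim is false for the complete procedure. This stands, and it limits the finding. It does not rescue Section 6.1, which attributes the power to a per-comparison alpha of 0.05 and not to the graph. Nor does the visible text of Section 6.6 say that alpha from the 4-mg branch reaches the 2-mg primary hypothesis.

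A second point is that Section 6.1 declares its alpha openly, the arithmetic is right at that alpha, and Section 6.2 prevents anyone from testing at the wrong level. All true: the defect is in the power rationale, not in the tests.

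A third is that little depends on it. The primary objective is met by either dose, and rewording a power rationale in a version approved shortly before database lock changes no analysis. The practical effect is indeed small, but a power claim for a primary hypothesis should still match the level at which it is tested.

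Finally, the planned test is Firth logistic regression with covariates, so all the figures above are unadjusted approximations. That is correct. It affects the decimals; the spread across methods in Step 4 makes it unlikely to close the gap at 0.01.

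**Conclusion.** The concern holds. The 2-mg power in Section 6.1 rests on an alpha that Section 6.6 does not initially give that hypothesis. At the allocated 0.01, power is about 86% (84.3% by Fisher, 79.7% to 86.5% across methods), against the stated more than 90%. The 4-mg claim is unaffected.

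These figures rest on the SAP's own response rates and arm sizes and on unadjusted tests. Under the full procedure, 2-mg power could lie anywhere from the no-recycling figure (86.5% Pearson, 84.3% Fisher) to the full-return figure (95.3% and 94.3%). Where it falls depends on weights not visible here. The finding does not show that the sample size is inadequate. It should be corrected because it concerns a primary hypothesis and the correction is cheap.

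**What to change.** In Section 6.1, replace the statement that both comparisons are powered at 0.05 with power at the Section 6.6 starting levels, for example: *With 240 placebo patients and 120 per baricitinib group, and response rates of 10%, 25% and 30%, power is about 99% for 4-mg at two-sided alpha 0.04 and about 86% (84% by Fisher's exact test) for 2-mg at two-sided alpha 0.01.* Name the test behind each figure and say that it approximates the planned logistic regression.

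Then add the 2-mg power under the complete graphical procedure, simulated with the Figure JAHM.6.1 weights and the shared placebo arm. If that exceeds 90%, the claim can stay, attributed to the graph.

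The cost is a few sentences and one short simulation. The stated 2-mg power may become less favourable. Enrolment, tests, alpha levels and decision rules do not change.
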